6.1 Disposition of Subjects

Subject disposition will be summarized by treatment group and overall. The following will be summarized:

- The number of patients screened
- The number of patients randomized
- The number of patients (%) in the Full Analysis set
- The number (%) in the Safety Analysis set
- The number (%) completing the study treatment
- The number (%) discontinuing the study treatment and the reasons for discontinuation of study treatment by Week 48 and by end of study
- The number (%) discontinuing the study and the reasons for discontinuation of study by Week 48 and by end of study

Subject disposition will also be summarized separately for each study site. Subject completion status, date of study completion/discontinuation, study day of discontinuation, and reason for discontinuation will be listed.

Patients who did not meet inclusion or exclusion eligibility criteria will be listed.

6.2 Demographic and Other Baseline Characteristics

[figure not shown]
6.2.1 Demographics and Baseline Characteristics

The following demographics, baseline characteristics, and randomization stratification variables will be summarized by treatment group and overall.

Demographics:

- Sex
- Age continuous and by category (<65, ≥ 65 , <75, ≥ 75 , 65-74, 75-84, >85 years)
- Ethnicity
- Race

Randomization stratification variables:

Other baseline characteristics:

• Systolic and diastolic blood pressure

Other Baseline Ocular Characteristics:

- BCVA: continuous
- Intraocular pressure in the study eye, continuous and by category (≤21, 22-29, >29 mmHg)
- Lens status (aphakic, pseudophakic, phakic)

Ocular Imaging, OCT:

• Center Subfield Thickness (CST)

Individual patients' demographics and baseline characteristics will be listed.

6.2.2 Ocular and Other Medical History

Medical history includes non-ocular events and ocular events for the study and fellow (nonstudy) eyes. Medical history will be coded using the Medical Dictionary for Regulatory Activities (MedDRA) [version 23.1] and will be summarized by System Organ Class (SOC) and Preferred Term (PT) for the Safety Analysis Set. Summaries will be presented by treatment group and overall. Two listings will be provided: one listing for all non-ocular medical history and an additional listing for ocular history by treatment, subject, and study/non-study eye.

6.2.3 Prior and Concomitant Medications/Procedures

All medications (ocular and non-ocular) will be coded using the World Health Organization (WHO) Drug Global Dictionary, Format B3 [Version September 2020 (or a later version if updated during the study)], Anatomical Therapeutic Chemical (ATC) Classification codes. Medications will be summarized by treatment group and overall for the Safety Analysis Set. Medication summaries will be presented by Anatomical Therapeutic Chemical (ATC) class level 4 and preferred name. In addition, ocular medications will be presented separately for the study eye and fellow eye.

Prior medications and concomitant medications are defined as follows:

- Prior medications are those taken prior to the start of the first dose of study treatment
- Concomitant medications are those with
- o a start date on or before the last dose of study treatment and
- $\circ~$ a stop date after the first dose of study treatment or are ongoing at the end of the study

See Section 5.2 for imputation of missing or partial dates.

Prior and concomitant medications will be separately summarized by ocular and non-ocular for the Safety Analysis Set as follows:

- The number and percentage of patients with at least one prior / concomitant medication / procedure will be presented.
- The number and percentage of patients with at least one prior / concomitant medication / procedure within each ATC Level 4, and preferred name will be presented.

- Patients reporting use of more than one medication / procedure at each level of summarization (any medication received, ATC class, and generic drug name) will be counted only once.
- The summary will be sorted using numerical counts by descending order of Therapeutic Subgroup, then descending order of preferred name in the KSI-301 group. Where groups or terms tie will be sorted by descending order in the sham group, then alphabetically.

Prior medications and concomitant medications (ocular and non-ocular) will be listed separately for the Safety Analysis Set.

The following will be summarized and listed for concomitant medications and procedures:

- Ocular (study eye and fellow eye separately) and non-ocular concomitant medications that were initiated *before* start of treatment.
- Ocular (study eye and fellow eye separately) and non-ocular concomitant medications that were initiated *after* the start of treatment.
- Medications prescribed after study treatment discontinuation for patients who remain in the study will be listed separately.
- Concomitant ocular procedures (study eye and fellow eye separately) administered while patients were on study treatment will be summarized and listed.
- Concomitant study eye procedures administered after study treatment discontinuation for patients who remain in the study will be listed separately.

In the listings the relative start and stop day of prior / concomitant medication (ocular and nonocular) use will be calculated relative to the first dose date of study treatment and will be presented for those patients who received at least one dose of treatment. If the concomitant medication is "Ongoing" it will be indicated as such in the listing and the relative stop day will not be calculated. Only original dates will be presented in the listing even though the relative day may be based on an imputed date.

6.3 **Protocol Deviations**

All major protocol violations will be determined and categorized by the timing of analyses (see Section 4.0):

• From start of the study to the data freeze for the Week 48 Primary Analysis

Major protocol deviations will be summarized by treatment group and overall, for the Full Analysis set. The number and percentage of patients with any major protocol deviation as well as the number and percentage of patients with deviations within each category of major deviation will be presented. The major protocol deviations will also be summarized by site. Protocol deviations will be listed in a subject data listing.

7.0 EFFICACY ANALYSES

7.1 Primary Efficacy Analysis

7.1.1 Primary Estimand

7.1.1.1 Target Population

The population targeted by the scientific question is treatment-naïve patients with moderately severe or severe NPDR.

The most relevant aspects of the study eligibility criteria for defining this population include the following key inclusion and exclusion criteria:

Inclusion criteria

- 1. Participants with moderately severe to severe NPDR in the Study Eye (DRSS levels 47 and 53 as determined by the reading center based on color fundus photographs), who have not previously received intravitreal medications for DR or DME, and in whom pan-retinal photocoagulation (PRP) can be safely deferred for at least 6 months per the Investigator.
- 2. BCVA ETDRS letter score in the Study Eye of ≥ 69 letters (approximate Snellen equivalent of 20/40 or better) in the Study Eye at Screening and confirmed at Day 1.

Exclusion criteria

- Presence of center-involved DME in the study eye, defined for this purpose as CST of ≥320 microns on SD-OCT (Heidelberg Spectralis or equivalent value on other OCT instruments).
- 2. Prior PRP in the Study Eye.
- 3. Current anterior segment neovascularization (ASNV), vitreous hemorrhage, or tractional retinal detachment in the Study Eye.

7.1.1.2 Primary Efficacy Endpoint/Variable of Interest

The primary efficacy variable of interest is DRSS, a categorical variable measured at each study visit by the reading center based on color fundus photographs. The primary efficacy endpoint is the proportion of eyes improving ≥ 2 steps on DRSS from baseline at Week 48.

7.1.1.3 Hypotheses and Test

The following hypothesis for the primary efficacy variable regarding the proportion of patients with a \geq 2-step improvement from baseline in DRSS score in the study eye at week 48 will be conducted to demonstrate the superiority of the KSI-301 group compared to the sham group.

The hypothesis to be tested is:

 $H_0: p_k - p_s = 0 \qquad \qquad vs \qquad H_1: p_k - p_s \neq 0$

Where p_k and p_s are the true proportions of patients with a ≥ 2 -step improvement from baseline in DRSS score in the study eye at week 48 in the KSI-301 and sham groups, respectively. The primary efficacy endpoint will be tested at the significance level of $\alpha = 0.0498$.

7.1.1.4 Intercurrent Events

The following intercurrent events (ICEs) may impact the assessment of the primary efficacy endpoint:

- 1. Treatment misallocation at 1 or more study visits.
- 2. Use of prohibited medications in the study eye.
- 3. Development of sight-threatening complication(s) and initiation of open-label KSI-301 5 mg treatment, panretinal photocoagulation, or other treatment for DME, ASNV, and/or PDR.
- 4. Premature discontinuation from study treatment due to study eye adverse events or due to lack of efficacy.
- 5. Premature discontinuation from study treatment due to events unrelated to study treatment such as malignancies, systemic infections, trauma, or other systemic adverse events that are not treatment-related, including discontinuations due to COVID-19.

Intercurrent events will be classified by the Sponsor prior to treatment code unmasking to prevent potential bias. Intercurrent events and the time to intercurrent events will be tabulated and listed by treatment group. Strategies for addressing the potential impact of these intercurrent events are described below.

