6.8.1 Pan-retinal Photocoagulation

Pan-retinal photocoagulation (PRP) laser is permitted in the Study Eye if PDR or ASNV develops. PRP will be reported as a concomitant procedure in the appropriate eCRF.

6.8.2 **Prohibited Therapy**

At the discretion of the Investigator, during the Study participants may start or continue to receive all medications and standard treatments administered for other conditions, except for the following:

- Investigational therapies in the non-Study Eye;
- Intravitreal anti-VEGF drugs other than study-assigned KSI-301 in the Study Eye;
- Systemic anti-VEGF therapy;
- Intravitreal or periocular steroids or steroid implants in the Study Eye;

- Concurrent use of macular laser photocoagulation in the Study Eye; and
- Investigational treatment with any drug (other than vitamins and minerals) or device.

Participants whose medical care requires use of a prohibited therapy must have study treatment interrupted or be discontinued from the study in order to receive that therapy. After discussion with the Sponsor, participants whose study treatment has been interrupted but no longer need a prohibited therapy may resume study treatment.

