This analysis will follow the same 'Hypothetical' strategy for handling of intercurrent events and analysis method as the primary analysis, with the exception that patients with the following significant protocol deviations will be excluded from the analysis: deviation from key inclusion/exclusion criteria as defined in Section 7.1.1.1, treatment misallocation at 1 or more study visits by Week 48, and use of prohibited medications in study eye at any point by Week 48.

7.1.5 Sensitivity Analysis 3

This analysis will follow the same 'Hypothetical' strategy for handling of intercurrent events and analysis method as the primary analysis, with the exception that patients with baseline DRSS level outside of levels 47 and 53 will be excluded from the analysis.

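### The intercurrent-event list omits treatment stops for treatment-related systemic adverse events, and omits systemic anti-VEGF therapy unless treatment is stopped for an unrelated illness

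*SAP*

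**What the plan says.** SAP 7.1.1.4 names five intercurrent events for the primary endpoint. Event 1 is treatment misallocation. The other four are:

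- Event 2: "Use of prohibited medications in the study eye".
- Event 3: development of a sight-threatening complication with the start of open-label KSI-301 5 "mg treatment, panretinal photocoagulation, or other treatment for DME, ASNV, and/or PDR".
- Event 4: "Premature discontinuation from study treatment due to study eye adverse events or due to lack of efficacy".
- Event 5: "Premature discontinuation from study treatment due to events unrelated to study treatment such as malignancies, systemic infections, trauma, or other systemic adverse events". The systemic events are qualified as "other systemic adverse events that are not treatment-related, including discontinuations due to COVID-19".

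SAP 7.1.2 (primary analysis) replaces measurements after a listed event by LOCF. Without a listed event the observed Week 48 grade counts, and LOCF is used only if that grade is missing or non-gradable. Sensitivity Analysis 1 makes every participant with a listed event by Week 48 a non-responder and leaves the others as in the primary analysis. Sensitivity Analysis 2 (SAP 7.1.4) excludes, among others, participants with "use of prohibited medications in study eye at any point by Week 48".

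Protocol 6.8.2 prohibits more than study-eye medications. Its list includes "Systemic anti-VEGF therapy", with no reference to an eye, and "Concurrent use of macular laser photocoagulation in the Study Eye; and" other items. A participant who needs a prohibited therapy must have study treatment interrupted or leave the study, and treatment may later resume. SAP Section 10 gives the SAP's intercurrent-event strategies precedence over the protocol, so protocol text does not fill a gap in the list.

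**The concern.** Under a composite strategy, stopping treatment because the treatment caused harm is usually among the first outcomes counted as failure. Here the list works the other way: an unrelated systemic stop is a failure and a treatment-related one need not be. The SAP gives no reason for the difference.

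The documents foresee the category. Protocol Table 2 names arterial thromboembolic events and hypersensitivity as risks, Protocol Appendix 3 has causality recorded as related or not related, and SAP 8.2 tabulates related non-ocular events. Protocol 7.1 encourages participants who stop treatment to attend Week 48, so gradable photographs after the stop may well exist.

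The limit to study-eye medications raises a separate problem. A therapy prohibited because it can act on the outcome can leave the participant scored on the observed grade, as if it had not been given. Sensitivity Analysis 2 repeats the limit and so does not repair it. The Per Protocol set in Protocol 9.3 removed participants for any prohibited medication, with no eye limit, but the SAP does not retain that set.

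**Working it through.** The finding rests on comparing texts. The cases below are set against events 2 to 5 and then against the rules in SAP 7.1.2 and 7.1.3.

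| Case before Week 48 | Listed event? | Primary analysis | Sensitivity Analysis 1 |
|---|---|---|---|
| Treatment stopped after trauma | Yes, event 5 | LOCF from the stop | Non-responder |
| Treatment stopped for a treatment-related systemic event | No: not study-eye (event 4), not unrelated (event 5) | Observed grade if present | Can be a responder |
| Systemic anti-VEGF, study treatment stopped for the unrelated illness | Yes, event 5 | LOCF from the stop | Non-responder |
| Systemic anti-VEGF, study treatment interrupted or continued | No: not in the study eye (event 2); interruption is not an event | Observed grade if present | Can be a responder |
| Macular laser for DME after a sight-threatening complication | Yes, event 3 (other treatment for DME) | LOCF from the event | Non-responder |
| Macular laser without such a complication | No: a procedure, not a medication (event 2); no complication (event 3) | Observed grade if present | Can be a responder |

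An example of the last row is edema below the DME limits in Protocol Table 3: CST of 320 to 349 microns without a 5-letter loss.

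**Reach.** SAP 7.2.1 repeats the wording of events 2, 4 and 5, 7.2.2 refers back to 7.1.1.4, and 7.2.3 refers back to 7.2.1. None of the three has a composite analysis. The only sensitivity analysis there, for 7.2.2, concerns baseline DRSS level. The gaps therefore reach these endpoints only through which data are used after the event.

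**Size per participant.** With about 120 per arm (SAP Section 9), one participant whose responder status changes moves that arm's rate by 1/120 = 0.83 points, three by 3/120 = 2.5 points, and five by 5/120 = 4.2 points. A participant who is a non-responder under either rule moves nothing, so 0.83 is a ceiling.

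**Illustration for Sensitivity Analysis 1.** The assumed response rates and the dropout rate are blacked out, so the planned 240 cannot be reproduced; the finding does not depend on it. The rates below are assumptions. For an unstratified two-proportion test with n = 120 per arm, two-sided alpha 0.0498 (z = 1.962), difference d and mean rate m:

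power = Φ{[d√n − z√(2m(1−m))] / √[p1(1−p1) + p2(1−p2)]}

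- 15% v 34%: (0.19 × 10.954 − 1.962 × 0.608)/0.593 = 1.50, power 93.3%.
- Three KSI-301 responders become non-responders, 15% v 31.5%: (0.165 × 10.954 − 1.962 × 0.597)/0.586 = 1.08, power 86.1%. With five, it is 79.0%.
- 15% v 45%: 99.95% with none, 99.8% with three, 99.6% with five.

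A few participants would matter near the smallest detectable effect and hardly at all for a large one.

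**The case against.** Much can be said for the plan as written.

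- The primary analysis changes little. A participant who stops and leaves the study gets LOCF whether or not the stop is listed. A difference needs someone who stays, has a later gradable photograph, and has a different responder status at Week 48 from that before the stop. For a KSI-301 eye whose effect wanes off drug, the observed grade would be the conservative choice.
- Such cases may be rare. Recent myocardial infarction or stroke, known hypersensitivity and most recent cancer are excluded at entry. Hypersensitivity seen as severe intraocular inflammation would be a study-eye event under event 4.
- They will be visible. The SAP tabulates stop reasons, concomitant medications, procedures and major deviations, and the sponsor classifies events before unmasking.
- The list has other unclear places, such as stops for non-compliance or pregnancy, which the rewording below does not settle.

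All of this stands. It limits the consequence, but it does not explain why a related systemic stop should be treated more leniently than an unrelated one.

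A reader might also infer more than the documents support. The list is not narrower than a list in the protocol, which defines no intercurrent events; the comparison is with its prohibited-therapy rule. Macular laser does not escape altogether, since event 3 covers it once a sight-threatening complication develops. The composite distortion does not extend to the key secondary endpoints. Nor do the gaps all favor KSI-301: systemic anti-VEGF in sham eyes would tend to raise the sham rate and work against it.

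**Conclusion.** The list has two real gaps, and they should be closed. The clearer one is the treatment-related systemic stop, where the stated rule in Sensitivity Analysis 1 classifies participants perversely. It would favor KSI-301 only if such stops were commoner among participants in that arm who would otherwise be responders; masked investigators can also judge events in sham participants as related. The second gap is systemic anti-VEGF without a stop for unrelated illness, plus the narrow case of laser without a complication.

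The effect is at most 0.83 points in an arm per participant, and only where responder status changes. That figure assumes about 120 analyzed per arm. The total effect cannot be determined from the documents and may be zero. Nothing here shows that the primary result is biased toward KSI-301.

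**What to change.** Make three wording changes to the SAP before unmasking:

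1. Event 4: premature stop *due to any study-eye adverse event, any treatment-related adverse event (ocular or systemic), or lack of efficacy*.
2. Event 2: *use of any therapy prohibited in Protocol 6.8.2 that can affect the study eye, including systemic anti-VEGF and macular laser*.
3. Carry the event 2 wording to Sensitivity Analysis 2, and both wordings to SAP 7.2.1. Sections 7.2.2 and 7.2.3 then follow by cross-reference.

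If either omission is deliberate, the SAP should give the reason instead. The cost is the SAP text and a masked re-review of concomitant medications, procedures and stop reasons already collected. No new data are needed, and no rule of clinical management changes.

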7.1.2 Analysis of Primary Efficacy Endpoint

The primary efficacy endpoint will be estimated based on the FAS, i.e., all randomized subjects who received at least one treatment injection and have gradable DRSS value at baseline.

The statistical analysis will be performed using the Cochran-Mantel-Haenszel (CMH) method,

A 'Hypothetical' strategy will be applied for all intercurrent events where measurements after occurrence of intercurrent event will be imputed using the last observation carry forward (LOCF) procedure. For patients who develop sight-threatening complication(s) and have non-gradable value at their first visit where open-label treatment is administered, the non-gradable values will be imputed as no change from baseline. For patients without intercurrent event, missing and non-gradable values at Week 48 will be imputed using LOCF. Baseline will be carried forward if all post-baseline observations are missing or non-gradable. Non-gradable values are observations where DRSS level is 90.

The p-value will be reported for comparison between KSI-301 and sham groups. In addition, the weighted percentages difference between the KSI-301 and sham (i.e., KSI-301 – sham) and 95.02% CI of the difference will be presented. Percentages are calculated as 100×number of "responders"/number of patients in FAS. Weighted percentages are based on weighted average of observed estimates across strata using CMH weights. The CI are based on the normal approximation to the binomial proportions.

The CMH method as described for the primary efficacy analysis will be used for all sensitivity analyses below.

7.1.3 Sensitivity Analysis 1

In this analysis, a 'Composite' strategy will be applied for all intercurrent events where patients with occurrence of intercurrent event by Week 48 will be considered as non-responders. For patients without intercurrent event, missing and non-gradable values at Week 48 will be imputed using LOCF, and baseline will be carried forward if all post-baseline observations are missing or non-gradable as in the primary analysis.

7.1.4 Sensitivity Analysis 2

This analysis will follow the same 'Hypothetical' strategy for handling of intercurrent events and analysis method as the primary analysis, with the exception that patients with the following significant protocol deviations will be excluded from the analysis: deviation from key inclusion/exclusion criteria as defined in Section 7.1.1.1, treatment misallocation at 1 or more study visits by Week 48, and use of prohibited medications in study eye at any point by Week 48.

7.1.5 Sensitivity Analysis 3

This analysis will follow the same 'Hypothetical' strategy for handling of intercurrent events and analysis method as the primary analysis, with the exception that patients with baseline DRSS level outside of levels 47 and 53 will be excluded from the analysis.

